7. OUTCOME MEASURES

7.1 Main outcome

The primary outcome will be a tympanometric measure. Tympanometric resolution in ears will be defined as conversion of the B-type highly predictive of effusion to either an A or C1 type i.e. back to normal pressures. Type C2 will not be considered sufficiently cured or resolved because the PPV for effusion of C2 remains modest at 55%.³⁴

The difference in proportions of children showing resolution to A or C1 in at least one B (affected) ear per child at one month is the main study outcome.

This outcome is chosen based on evidence from the Cochrane review and hence is the basis for the sample size calculation. It is also a robust outcome and less likely to be affected by any placebo effect of intervention. Otoscopy will be performed by the trained nurse prior to tympanometry to improve method validity. Nurses will attend a day course that includes full relevant instruction in practical tympanometry procedures and will use a learning-set of tympanogram print outs to categorise type before collecting data as a training aid. The MTP-10 micro-tympanometers used (sufficient stock is available from the recent GNOME trial) are being serially re-calibrated for the proposed new trial and all have a print out facility. A central trial fax-hotline will be used for tympanogram interpretation in the study for "at-point-of-care" support, and will be the basis for continuing training of operators to improve repeatability and validity of the method. (Tympanometric skills will be assessed in initial samples of consecutive cases per nurse-operator).

Difference in tympanometric baseline severity is likely to be an effect modifier and will be accounted for in both the minimisation protocol and secondary analysis (see relevant sections).

7.2 Secondary outcomes

All measures will be assessed at baseline (0), and 1 and 3 months post baseline (except the OMQ-14, designed to collect retrospective 3 month data and TADAST which will be performed at baseline and 1 month only).

- The difference in proportions of children showing resolution to A or C1 in at least one B (affected) ear per child at 3 months
- OMQ-14 a functional health status measure that is a derivative of the OM8-30 that is both pragmatic and predicts QoL well, and will be self-administered at baseline and 3 months (please see Appendix 2). The main measurement tools have been used in GNOME with validation. The OMQ-14 is a succinct standardised and responsive 14 item measure that looks at the quality of life, physical and developmental impact of OME. It records the previous 3 month history including frequency of respiratory tract infections which is the main theoretical adverse event (see above). Together with a brief resource use questionnaire (used in GNOME) and notes audit, it will collect useful adjunctive health economic information.
- Parents will be asked to complete short study-specific questionnaires at the above times for evaluation of: compliance; positives/negatives of device; being in a study; NHS resource use for economic evaluation; and also use weekly symptom and adverse event diaries collected at 1 and 3 months to prospectively collect data on the main areas of OME clinical impact. The diaries record days with reported hearing loss and earache, as well as recording periods of remission and recurrence. The diaries make use of Likert scales for symptoms as validated and used in other studies from our group. 36,40,41
- Hearing will also be assessed by using the web TADAST speech recognition in noise parent supervised (self-complete) test at baseline and 1 month. 38,42,43 Audiometry will not be included to assess hearing level in this trial because hearing level is not a known effect modifier, it's correct use is somewhat variable and unreliable in primary care because of factors such as those associated with child age and type of test, operator training issues, and high background noise levels confounding the results. Measures based on reported hearing difficulty (OMQ-14 questionnaire) and air conduction estimates from tympanometry have however been developed which can be also used in the analysis. 15
- Health Utilities Index covering 4 weeks recall as used in GNOME trial and extensively validated in children.^{15,44,45,46}
- 6 month study specific questionnaire on health resource use including recurrence, referral etc. Done by nurse audit of records.

In the treatment group children whose ear(s) have not got fully better at 1 month (i.e. have a residual B type in at least one ear), will be offered (a further) two months of treatment using autoinflation. All children will be asked to return at 3 months for a final screening (and to enable a full ITT analysis).

8. STATISTICS AND DATA ANALYSIS

8.1 Sample size

For a discussion on the effect size estimated from the meta-analyses please see earlier sections. 20,21 We have chosen the most conservative estimate of effect size i.e. 2.4, and think it likely that earlier presentation of cases in primary care will be associated with more serous and less mucoid effusions, 39 so easier to clear by this method. The most recent study identified by Cochrane for an updated review showed a relatively large effect. The pilot also confirmed a relatively large effect from primary care OR 4, 95% CI 0.97 to 16.46. Standard power calculations using the NQuery programme have been performed based on objective tympanometric outcomes that define cure at 1 month. A 45% control cure rate at 1 month is anticipated in the calculations as found in the previous GNOME trial. The best estimates are based on a meta-analysis of 4 trials that use Otovent, to be included in the update for Cochrane 22,23,28 (with one unpublished trial outcomes data, cited). For cure at 1 month, the most conservative evidence based estimate of effect size is OR =2.4 Given this effect size we require 250 children (125 in each group) for a standard α =5% and power=90%. With 15% loss to follow-up, 295 are needed in total (for power=80%, 226 are needed in total). This sized sample will be able to detect a~0.3 SD difference on continuous effectiveness measures used in the study e.g. the OMQ-14 total scores, or days with hearing loss/otalgia or TADAST total score for functional hearing disability i.e. a small effect size. Differences of much less than this are not likely to be clinically significant.

8.2 Statistical Analysis

The main analysis will be an intention to treat analysis with individual children the unit of analysis rather than ears. Proportions of children cleared of one or more B type tympanograms (90% probability of effusion) at 1 month will be compared using a logistic regression model adjusting for the variables used in minimisation and other covariates as appropriate (including likely effect modifiers). Although not specifically powered to assess effect modification we will explore potentially important variables: interaction tests will be performed between randomisation groups and if statistically significant, subgroup results will be presented separately. From the GNOME trial only clinical severity was an effect modifier, however two interesting subgroups were noted on secondary analysis relating to age as a dichotomous outcome (>=6.5 years versus <6.5 years) and gender. Season and atopic status were not effect modifiers. Severity will include tympanogram readings (unilateral versus bilateral effusion), frequency of GP surgery attendance in the past 12 months for ear problems, and OMQ-14 score at baseline.

Logistic regression models will also be used for other dichotomous outcomes, and ANCOVA will be used for continuous variables adjusting for baseline differences and potential effect modifiers as appropriate. All estimates will be presented with 95%C.I.s. A trial analysis plan will be drawn up before the main trial starts.

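### Separate subgroup results are tied to a significant interaction test, with no commitment to show the rest, so the subgroup effects shown would be a significance-selected set

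*Protocol*

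**What the plan says.** Protocol section 8.2 introduces the subgroup work with a caveat: "Although not specifically powered to assess effect modification we will explore potentially important variables". It then gives the rule: "interaction tests will be performed between randomisation groups and if statistically significant, subgroup results will be presented separately".

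Five candidate modifiers can be read from the same section:
- Age and gender come from an earlier trial by the team, where "two interesting subgroups were noted on secondary analysis relating to age as a dichotomous outcome (>=6.5 years versus <6.5 years) and gender".
- Three are measures of severity: "Severity will include tympanogram readings (unilateral versus bilateral effusion), frequency of GP surgery attendance in the past 12 months for ear problems", plus the baseline OMQ-14 score.

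Two other sections treat some of these as prior hypotheses. Section 7.1 says: "Difference in tympanometric baseline severity is likely to be an effect modifier", and adds that severity will be handled in the minimisation and in secondary analysis. Section 2.3 expects the technique to work better in older children and lists age or head size as a possible modifier.

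On presentation in general, section 8.2 says: "All estimates will be presented with 95%C.I.s". It also promises an analysis plan before the main trial starts.

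**The concern.** Testing the interaction before interpreting subgroups is sound practice. The difficulty is that the test result also decides what is presented. In a trial with little power for interactions, a real but moderate one will usually miss significance. Under the rule as worded, its subgroup effects would then not be set out.

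Two things follow. The subgroup effects that do appear have passed a high threshold, so on average they overstate the difference between subgroups. For severity and age, where the protocol has a prior expectation, a reader could also be left without the interval that shows which interactions the data rule out. A later meta-analysis could not use those results. That matters here because sections 2.2 and 8.1 rest the case for this trial on pooling small studies.

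The rule is fixed in the protocol, so an analysis plan that followed it faithfully would inherit it.

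**Working it through.** **Inputs from the protocol.** Section 8.1 gives the control rate ("A 45% control cure rate at 1 month is anticipated in the calculations") and the effect ("the most conservative evidence based estimate of effect size is OR =2.4"). It also gives 125 evaluable children per group, alpha 5% and 90% power. Section 3.2.3 gives 1:1 allocation.

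**Inputs assumed, because section 8.2 does not state them.** Two-sided 5% for each interaction test; a binary modifier split 50/50 or 35/65; true ratios of subgroup odds ratios from 1 to 4.

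**Step 1: reproduce the plan's own sample size.** Intervention odds = 2.4 × 0.45/0.55 = 1.964, so the intervention rate is 1.964/2.964 = 66.3%. A two-proportion calculation with continuity correction gives 122 per arm, 244 in total, within 3% of the stated 250. Then 250/0.85 = 294.1, rounded up to the stated 295. The inputs are read correctly.

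**Step 2: standard error of the interaction.** For the log ratio of odds ratios between two subgroups, the variance is the sum of 1/[m·p(1−p)] over the four cells (arm by subgroup), where m is the cell size. With an even split, m = 250/4 = 62.5. For a true ratio of 2, centred on 2.4, the subgroup odds ratios are 2.4 × √2 = 3.39 and 2.4/√2 = 1.70. The intervention rates are then 73.5% and 58.1%.

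- Two control cells: 1/(62.5 × 0.45 × 0.55) = 0.0647 each
- Intervention cells: 1/(62.5 × 0.735 × 0.265) = 0.082 and 1/(62.5 × 0.581 × 0.419) = 0.066
- Variance = 0.277, SE = 0.527

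**Step 3: threshold and power.** Significance needs an absolute log ratio above 1.96 × 0.527 = 1.03, a ratio of about 2.8 in either direction. With a = 0.693/0.527 − 1.96 = −0.64, power is Φ(−0.64), about 26%.

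**Step 4: average estimate when significant.** The mean log estimate given significance is about [θΦ(a) + SE·φ(a)]/power = (0.693 × 0.260 + 0.527 × 0.324)/0.260 = 1.35. This is a ratio of about 3.9. Exaggeration on the log scale is 1.35/0.693 = 1.95 times. Simulation with 2,000,000 draws agrees.

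**Step 5: range.** The average ratio is the exponential of the mean absolute log estimate.

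| Split | True ratio | SE | Smallest ratio shown | Chance shown | Average ratio when shown | Exaggeration, log scale |
|---|---|---|---|---|---|---|
| 50/50 | 1 | 0.522 | 2.78 | 5% | 3.39 | – |
| 50/50 | 1.5 | 0.524 | 2.79 | 12% | 3.60 | 3.16 |
| 50/50 | 2 | 0.527 | 2.81 | 26% | 3.86 | 1.95 |
| 50/50 | 3 | 0.534 | 2.85 | 54% | 4.44 | 1.36 |
| 50/50 | 4 | 0.541 | 2.88 | 73% | 5.12 | 1.18 |
| 35/65 | 1.5 | 0.552 | 2.95 | 11% | 3.84 | 3.32 |
| 35/65 | 2 | 0.557 | 2.98 | 24% | 4.13 | 2.05 |
| 35/65 | 3 | 0.567 | 3.04 | 49% | 4.75 | 1.42 |
| 35/65 | 4 | 0.577 | 3.10 | 67% | 5.45 | 1.22 |

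Power of 80% would need a true ratio of about exp(2.8 × 0.541) = 4.5 with an even split, and about exp(2.8 × 0.577) = 5.0 at 35/65.

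**Step 6: multiple testing, kept separate.** With independent tests at 5%, the chance of at least one false signal is 1 − 0.95³ = 14% for three factors and 1 − 0.95⁵ = 23% for five.

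**The case against.** The strongest reply is that the sentence does not contain the word *only*. The tests are to be done unconditionally. The condition attaches to separate presentation, and nothing forbids tabulating the other interactions. Section 8.2 promises intervals for all estimates, labels the work as exploration and defers to an analysis plan. Section 7.1 says severity will be taken into account without any significance condition. The protocol itself mentions season and atopic status as null modifiers in earlier work.

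Some of this stands. A reader might infer that the protocol forbids showing null interactions, or that severity is bound to go unreported. The text says neither. Because the candidate factors are named in section 8.2, a reader of the protocol can also tell which were meant to be examined. But the promise of intervals governs the form of the estimates, and taking severity into account is not a commitment to show its interaction. A condition with no alternative branch is naturally followed as a filter.

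Two further inferences go too far:
- **That every subgroup effect shown would be a chance finding or inflated.** Inflation is an average. In the even-split case, the share of significant estimates below the truth is about (0.539 − 0.5)/0.539 = 7% at a true ratio of 3 and (0.727 − 0.5)/0.727 = 31% at 4.
- **That the rule causes the 14–23% chance of a false signal.** That comes from running several tests and would be the same under full reporting. It also assumes independence, which is doubtful because three of the five factors measure severity.

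Full reporting would not shrink a significant estimate either. It removes the selection from the reported set, so the estimate can be read beside the others.

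**Conclusion.** The concern holds as a fault in a stated reporting rule. Followed as written, section 8.2 yields subgroup effects selected on significance, in a trial that says it lacks power for them. Across the true ratios of 1.5 to 4 and the splits examined, the average exaggeration among those shown is about 1.2 to 3.3 times on the log scale. A moderate interaction (ratio 2) would go unshown about three times in four.

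These sizes rest on the assumed interaction sizes, splits and 5% level. GP attendance and OMQ-14 need not be split in two, so for those the figures are only indicative. The effect is confined to exploratory subgroup reporting and any later pooling. The primary intention-to-treat comparison and the sample size do not change. The correction is worth making because it is cheap, not because the main conclusion is at risk.

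**What to change.** In section 8.2, replace the conditional clause with wording such as:

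> For each pre-specified modifier (laterality, GP attendance for ear problems, baseline OMQ-14, age, gender), the interaction estimate with 95% CI and p-value, and the subgroup effects, will be reported whatever the result. The number of tests will be stated and all will be labelled exploratory.

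The analysis plan should carry the same sentence and say how GP attendance and OMQ-14 enter the model, since the protocol gives a cut-point only for age. The interaction test stays as the guide to interpretation.

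The cost is one sentence and one extra table or forest plot. No new data are needed and the sample size is unchanged. The estimates will remain imprecise (SE of the log ratio about 0.52 to 0.58), which the intervals will show.

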8.3 Economic analysis

The primary analysis will take a health service perspective. The primary economic analysis will be for a 3-month follow up although the Otovent device will also be evaluated at the 1-month follow-up stage. We will measure OME associated resource use including the cost of providing the Otovent device to the treatment group and any OME related health care use in the follow up period (both groups). Healthcare use will be measured by means of GP case note review using a specially designed data collection proforma. This will be collected for all subjects and will include the three month follow up period and also a 12-month period before randomisation to test the equivalence of the study groups for resource usage. Resource use will also be collected for the 3-6 month follow up period. In addition, a parent/carer completed questionnaire will be used to obtain details of any relevant family borne costs as well as any time off work required because of the child's OME, which will enable a societal viewpoint to be taken for costs. Resource use will be costed using appropriate recent local and national cost data, including costs of health and community care, ⁴⁷prescribing costs from the BNF, ⁴⁸ and NHS reference costs (DoH 2008). ⁴⁹

Two types of outcome measure will be used in the economic evaluations. Firstly, the number of children with tympanometric resolution of OME, at both 1 and 3 months post-randomisation. This will contribute to a cost-effectiveness study calculating the cost per additional child with resolved OME. The second measure will be the Health Utilities Index (HUI), using parents/carers as proxies. This will be collected at baseline 1 and 3-months, and these values will be used to estimate quality adjusted life years (QALYs) for the three month period by means of area under the curve. The incremental cost per QALY will be estimated for the Otovent group compared to the control group for a cost-utility study. The Health Utilities Index (HUI) has been widely used in children, and has been used in an evaluation of OME in children in the UK.¹⁵

Data will be analysed using appropriate statistical techniques such as non-parametric bootstrapping. We will investigate the effect of any differences in baseline characteristics (e.g. costs, age, gender) on results and if necessary will use regression methods to control for these. If there are problems with missing data we will use appropriate statistical techniques to impute values, for example multiple imputation. If this is used we will present results with and without imputed values. Where appropriate we will estimate incremental costs and benefits, incremental cost-effectiveness ratios (ICERs), and cost-effectiveness acceptability curves. A sensitivity analysis will be carried out to examine the effect of assumptions made in the analysis. This will include scenario analysis using the results from the trial in addition to data from other sources to model the longer term cost-effectiveness of the Otovent device. Resource use data from the 6 month audited follow up period (using a study proforma) will also be used to inform these scenario analyses.

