3.2.4 Randomisation

If the trained research nurse assesses that the child is likely to be able to use the device they will be offered randomisation. To ensure the generator and executor processes are fully independent in relation to randomisation (and avoid subversion) we will employ an external agency to provide a web-based randomised selection method to participating trial nurses who will access a preloaded website on their computer. Nurses will be trained in use of the website and have further access to support. Randomisation will be overseen by the Primary Care Clinical Trial Unit located at Oxford. A standard minimisation protocol will be used based on three potentially important variables: age (>=6.5 years versus <6.5 years); baseline severity (1 versus 2 B type tympanograms); and gender. 15

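### Section 8.3 leaves adjustment of the QALY difference for baseline HUI optional and without a criterion, although baseline HUI is part of the QALY

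*Protocol*

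**What the plan says.** Section 8.3 of the protocol schedules the HUI at three visits, baseline and both follow-ups. On the QALY it then says that "these values will be used to estimate quality adjusted life years (QALYs) for the three month period by means of area under the curve". The result is the denominator of the cost-utility ratio: "The incremental cost per QALY will be estimated for the Otovent group compared to the control group".

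Later in the same section comes the adjustment rule: "We will investigate the effect of any differences in baseline characteristics (e.g. costs, age, gender) on results and if necessary will use regression methods". For resource use, section 8.3 also reviews the year preceding entry to the trial, with the stated purpose "to test the equivalence of the study groups for resource usage". It plans no similar baseline comparison for utility.

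Two other places bear on the point. Section 3.2.4 minimises on "age (>=6.5 years versus <6.5 years); baseline severity (1 versus 2 B type tympanograms); and gender", so HUI is not balanced by design. Section 8.2, in the clinical analysis, says that "ANCOVA will be used for continuous variables adjusting for baseline differences and potential effect modifiers as appropriate". That sentence is itself conditional and does not mention QALYs.

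**The concern.** Baseline HUI enters the QALY twice. It is the first point of the curve, which treatment cannot change, and it predicts the two later points. A chance difference between arms at baseline therefore passes into the unadjusted QALY difference and on into the cost per QALY.

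The rule in section 8.3 leaves the response to that open. The analyst looks at the differences and their effect on the results, then decides whether to adjust, with no stated threshold. Two of the three examples given, age and gender, are already minimisation factors. The covariate most closely tied to the QALY is not mentioned.

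Two things are at stake: precision in a comparison over a quarter of a year, where any QALY gain is small in absolute terms, and the credibility of a result whose adjustment was chosen after the data were seen.

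**Working it through.** **The plan's own figure.** The protocol gives no SD, correlation or target difference for HUI or QALYs. The only stated figure that sets the size of a chance imbalance is the 125 per group in section 8.1. It can be checked:
- Control rate 45%, odds ratio 2.4: odds = 2.4 × 0.45/0.55 = 1.964, so the intervention rate is 1.964/2.964 = 66.3%.
- Two-sided 5% (sidedness assumed) and 90% power give 113 per arm without and 122 per arm with continuity correction. The corrected total, 244, is close to the stated 250.
- 250/0.85 = 294.1, which rounds up to the stated 295.

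So 125 per arm is a fair input.

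**Assumed inputs.** HUI SD 0.15 (range 0.10 to 0.20), the same at each visit. Correlation r = 0.6 (range 0.4 to 0.8), the same between every pair of visits. HUI complete in 125 children per arm.

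**Step 1: area-under-the-curve weights** (trapezium rule, visits at 0, 1 and 3 months).
- Baseline: 0.5 month = 1/24 year = 0.0417
- Month 1: 1.5 months = 0.125 year
- Month 3: 1.0 month = 0.0833 year
- Sum: 0.25 year. The baseline share is 0.5/3 = 1/6. This step needs no assumption about HUI.

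**Step 2: chance imbalance.** SE of the baseline difference = SD × √(2/125) = 0.1265 SD. At SD 0.15 this is 0.0190.

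**Step 3: shift in the unadjusted QALY difference from a one-SE imbalance.** Shift = (0.0417 + 0.2083 r) × SE.
- SD 0.15, r 0.6: 0.1667 × 0.0190 = 0.0032
- SD 0.10, r 0.4: 0.1250 × 0.0126 = 0.0016
- SD 0.20, r 0.8: 0.2083 × 0.0253 = 0.0053

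**Step 4: comparison with the unadjusted SE.** The variance of one child's QALY is SD² × [Σw² + 2r Σww′], where Σw² = 0.02431 and the sum of the three cross-products is 0.01910.
- At r 0.6 the bracket is 0.02431 + 1.2 × 0.01910 = 0.04722.
- Unadjusted SE = √(0.016 × 0.0225 × 0.04722) = 0.0041.
- The shift is 0.0032/0.0041 = 0.77 of that SE.

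**Step 5: gain from adjustment.** Adjusted SE = √(0.0041231² − 0.0031623²) = √(0.0000170 − 0.0000100) = 0.0026, which is 0.64 of the unadjusted SE. This ratio does not depend on the SD. By the same formula:
- r 0.4: bracket 0.03958, explained share 0.125²/0.03958 = 0.39, ratio √0.61 = 0.78
- r 0.8: bracket 0.05486, explained share 0.2083²/0.05486 = 0.79, ratio √0.21 = 0.46

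**The case against.** The strongest defence is that nothing here is excluded. The rule covers any baseline difference, its examples are illustrative, and HUI is a baseline measurement. An imbalance that moved the cost per QALY is something the section undertakes to investigate. Section 8.2 also promises a separate analysis plan, which could fix the covariates. This stands in part: imbalance carries through only if the analyst decides not to adjust. But the protocol has not simply deferred the matter. It states a data-dependent rule, and an analysis plan that followed it would inherit that rule.

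Three stronger readings are tempting, and the document does not support them.
- **Systematic bias.** Randomisation keeps the unadjusted difference unbiased on average. The extra variation is already inside the unadjusted standard error and would appear in the planned bootstrap and acceptability curves. The loss is in precision and in conditional accuracy given the imbalance seen.
- **Chance imbalance could reverse the sign.** The protocol gives no expected QALY gain to compare against. If HUI truly rose by an assumed 0.03 at both follow-ups, the gain would be 0.03 × 0.2083 = 0.00625 QALY. Even the largest one-SE shift above, 0.0053, would not by itself turn that negative.
- **The shift is worth many times the device.** At an assumed £20,000 per QALY (not in the protocol), the shifts are worth about £32 to £105. The £7.20 in section 2.3 is for one month. Three packs cost £21.60, so the ratio is about 1.5 to 5, before nurse training and support are counted.

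**Conclusion.** The point holds as a weakness in a stated analysis rule. Section 8.3 builds baseline HUI into the QALY, yet makes adjustment for it discretionary and without a criterion. At the central assumptions an ordinary one-SE imbalance moves the estimate by roughly three quarters of its unadjusted standard error, and routine adjustment would remove about a third of that standard error.

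The one-sixth baseline weight is fixed by the visit schedule. The QALY shifts depend on the assumed SD and correlation, and the precision gain on the correlation alone. Equal correlation between visits and complete HUI data are simplifications.

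The reach is limited. The tympanometric primary outcome and the cost per additional child resolved do not use HUI and are untouched. The label is a free improvement to the cost-utility analysis.

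**What to change.** State in section 8.3 that the incremental QALY will be estimated by regression on trial arm, with baseline HUI and the three minimisation factors as prespecified covariates whatever imbalance is observed. Run this model within the bootstrap, and show the unadjusted result as secondary. Remove the conditional wording for baseline HUI. The argument does not require a change to the cost model, for which prior-year resource use is already collected and costs are already named.

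The cost is a sentence or two of wording and no new data, since sections 7.2 and 8.3 already place HUI at baseline. The Synopsis lists HUI at 1 and 3 months only and should be brought into line, so that the baseline assessment is not missed.
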